5.3 Patient Reported Outcome Measures

22-item Sino-nasal Outcome Test (SNOT-22):

The SNOT-22 score is a validated disease-specific questionnaire quantifying quality-of-life among participants with chronic rhinosinusitis. The individual question scores range from 0 (no problem) to 4 (as bad as can be) among 22 individual questions. The threshold value for minimal clinically significant change is ≥ 8.90 [8].

Asthma Control Questionnaire (ACQ) (only for participants with asthma):

The Asthma Control Questionnaire (ACQ) is a validated, self-administered survey used to assess a participants' perception of disease control over the preceding week using Likert scale responses (range: 0 - 6) [9]. The ACQ consists of 7 items surveying the frequency of asthma related symptoms, the need for rescue medications, and perceived control of disease. The items are equally weighted and the ACQ score is the mean of the 7 items and therefore between 0 (well controlled) and 6 (extremely poorly controlled)[9]. Score change of 0.5 on the 7-point scale has previously been defined as the Minimal Important Difference (MID).

6. Data Specimen Collection and Banking

There is no routine laboratory monitoring planned. If laboratory monitoring is needed to provide standard of care for participants, this will be performed and monitored. Whole blood will be collected for research purposes for metabolomic profiling and for preparation of serum and plasma samples for analysis of proteins and inflammatory markers. Nasal secretions will be collected for analysis of inflammatory markers at specified study visits. Blood samples and nasal secretions will be collected prior to IMP dosage (V1,3-5,7-8). Additionally, nasal polyps will be collected from all participants, concurrent with their sinus surgery and per SoC. Samples will be processed, frozen, and shipped to the central study repository ([name] Laboratory; Emory University, [name]).

The subject's consent to the collection and storage of biologic samples is optional. Samples will be collected for future, exploratory analysis to query the effect of dupilumab on biomarkers of upper and lower airway inflammation, NP recurrence and predictors of therapeutic response.

7. Inclusion and Exclusion Criteria

Each subject must meet all inclusion and none of the exclusion criteria for the study in order to be consented into the study; ie. enrolled. Further, each subject must continue to meet all inclusion and none of the exclusion criteria for the study post SoC surgery in order to be randomized to a study intervention. Participants who do not meet I/E requirements prior to randomization are screen failures (see section 9.3- Screen failures)

In this protocol, "enrolled" participants are defined as those signing informed consent. "Randomized" participants are defined as those undergoing randomization and receiving IMP.

7.1 Inclusion Criteria

Patients are eligible for study participation if all inclusion and no exclusion criteria are met. Non-English-speaking people will be included if they fulfill the criteria.

Version: 3.7.3 2Apr2024

7.1.1 Informed consent

- 1. Patients must be capable of giving signed informed consent as listed in the informed consent form (ICF) and this protocol.
- 2. ICF must be signed and dated prior to study specific procedures. Informed consent process is described in Appendix A3.

7.1.2 Age

3. Patients must be aged >18 years at the time of signing the ICF.

7.1.3 Types of subject and disease characteristics

- 4. Patients with nasal polyps in the setting of suspected AFRS and electing to undergo comprehensive sinus surgery per established criteria. [1, 4]
 - Diagnosis of nasal polyps by consensus criteria.
 - Failure of appropriate medical therapy, including topical intranasal corticosteroid (spray or irrigation) > 8 weeks duration, systemic corticosteroid trial of 1-3 weeks duration and nasal saline irrigation of > 4 weeks duration.
 - A minimum SNOT-22 score of 20 at time of enrollment.
 - A minimum CT Lund-MacKay score of > 1 at time of enrollment.
- 5. Suspected AFRS based on Bent and Kuhn criteria [10]
 - Patients must meet 3/5 criteria at time of enrollment
 - Environmental atopy by skin or serum testing
 - Nasal polyposis
 - Characteristic CT findings
 - Eosinophilic mucous
 - Fungal identification on histopathology
 - Patients must meet 5/5 criteria at time of randomization

Enrolled participants are expected to undergo SoC allergy testing and sinus surgery prior to randomization. This will complete evaluation for suspected AFRS, thus enabling further study participation.

7.1.4 Sinus Surgery

6. All study participants will have met criteria for sinus surgery and undergo a comprehensive surgery prior to randomization. The surgery will not be assigned and will be completed per SoC for the management of nasal polyps in suspected AFRS. [4]

7.1.5 Reproduction

- 7. Negative urine pregnancy test will be required at enrollment and study visits 3-8 throughout treatment period for female participants of childbearing potential (i.e., post-pubescent, premenopausal females).
- 8. Women of childbearing potential must use an effective form of birth control (confirmed by the Investigator) e.g., total sexual abstinence, vasectomized sexual partner, tubal occlusion, intrauterine device or levonorgestrel Intrauterine system, Depo-Provera injections, oral contraceptive, Evra Patch, or Nuvaring. Women of childbearing potential must agree to use a highly effective method of birth control, as defined above, from enrollment, throughout the study duration and for 12 weeks after the last dose of IMP.
- 9. To protect against possible side effects, men should not get a sexual partner pregnant while taking the study drug and for 13 weeks after the last dose. Men should agree on a method of birth control to use throughout the study.

7.2 Exclusion criteria

7.2.1 Medical conditions

- 1. Patients who have undergone nasal or sinus surgery within 3 months prior to enrollment.
- 2. Patients with conditions or comorbid disease findings that exclude nasal endoscopy for evaluation of primary outcome, such as:
 - Current rhinitis medicamentosa
 - Nasal cavity tumors
 - Occlusive septal deviation following surgery
- 3. Clinically important comorbidities that may confound interpretation of clinical efficacy, including:
 - Aspirin-exacerbated respiratory disease
 - Cystic fibrosis
 - Primary ciliary dyskinesia
 - Hereditary Hemorrhagic Telangiectasia
 - Antrochoanal polyposis
 - Non-asthma eosinophilic disease, such as bronchopulmonary aspergillosis, eosinophilic granulomatosis with polyangiitis, hypereosinophilic syndrome
 - Granulomatosis with polyangiitis
 - Any corticosteroid dependent condition
- 4. A comorbid health disorder that is not medically controlled in the opinion of the Investigator, and has the potential to:
 - Affect the safety of the subject throughout the study
 - Impede the subject's ability to complete the duration of the study
 - Influence the primary or secondary outcomes of the study
- 5. Patient experiencing a symptomatic asthma exacerbation requiring systemic corticosteroids or hospitalization (>24 hours) within 4 weeks of randomization.
- 6. Infection requiring systemic antibiotics within 4 weeks of randomization.
 - Parenteral and/or oral antibiotics associated with surgery are allowed (see Section 4.5.3-Postoperative care)
- 7. Medical contraindication to receiving dupilumab:
 - Know hypersensitivity to dupilumab or any of its excipients
 - Live vaccine administration within 30 days of randomization or during study period
 - Known helminth infection
- 8. Unable to tolerate sinonasal irrigations.
- 9. Pregnancy, current lactation, or lack of effective contraception plan, as determined by the site investigator.

7.2.2 Prior/concomitant therapy

- 10. Initiation of allergen immunotherapy within 3 months prior to randomization or a plan to begin therapy or change its dose during the study period.
- 11. Immunosuppressive medication within 3 months prior to randomization and during the study period from randomization through EOS.

Version: 3.7.3 2Apr2024

12. Receipt of any marketed or investigational biologic products (monoclonal or

- polyclonal antibody) within 6 months or 5 half-lives, whichever is longer, prior to randomization during the study period.
- 13. Previous use of dupilumab.
- 14. Receipt of immunoglobulin or blood products within 30 days prior to randomization.
- 15. Receipt of any investigational drug within 30 days or 5 half-lives, whichever is longer prior to randomization.
- 16. Scheduled systemic corticosteroid treatment during the study period:
 - Standardized corticosteroid taper associated with planned surgery is allowed (see Section 4.5.3-Postoperative care.)
- 17. Receipt of leukotriene antagonists or modifiers for participants who were not on a stable dose for > 30 days prior to randomization.

7.2.3 Prior/concurrent clinical study experience

18. Concurrent enrollment in another investigational drug trial during the study period.

7.2.4 Other exclusions

- 19. Patient involvement in the planning or conduct of the study.
- 20. Investigator assessment that the subject is unlikely to comply with study procedures.
- 21. Prior randomization in the present study.
- 22. Unable to undergo sinus surgery due to comorbid medical condition.

7.3 Screen Failures

Defined as participants appearing to qualify for study participation, sign the ICF, but ultimately do not meet randomization criteria. Reporting of screen failure information is required to ensure transparent reporting. Minimal information includes subject demographics, screen failure details and eligibility criteria.

Re-screening is allowed once for each subject.

Re-screening is allowed prior to surgery for transient reasons (including operating room availability or unforeseen personal events) that result in delayed randomization.

For participants who require oral corticosteroids and/or antibiotics for an asthma exacerbation or an acute exacerbation of CRS during the run-in period (prior to surgery), the run-in period may be extended for up to 6 weeks beyond the initially planned 6 weeks, provided the treatment duration with corticosteroids and/or antibiotics is \leq 14 days. If the duration of treatment is \geq 14 days, participants should be screen failed but can be considered for re- screening.

Re-screened participants should re-sign ICF. All procedures from the screening period should be repeated. Re-screening should be documented so that its effect on study results may be assessed.

8. Local Number of Participants

The study will be completed at 3 North American sites. A total of 132 participants will be randomized. While we intend to enroll equal numbers of participants from each site (44 participants at each), variability in available participants may require an unequal distribution of participants to support target enrollment within the study period.

Page 26 of 58 Version: 3.7.3 2Apr2024

9. Recruitment Methods

All three sites taking place in this research study will recruit participants who are undergoing elective endoscopic sinus surgery for the treatment of AFRS. The participants will be identified from the clinics of the site Investigators and their colleagues during the subject's pre-operative consultation.

10. Withdrawal of Participants

10.1 Discontinuation of study treatment

Participants may be discontinued from study treatment under the following circumstances:

- Subject decision. Participants may discontinue treatment at any time
- AE that, in the opinion of the Investigator, contraindicates continuation.
- Pregnancy
- IMP unblinding
- Development of any study specific criteria for discontinuation:
 - Anaphylactic reaction to the IMP requiring epinephrine
 - Helminth parasitic infestations requiring hospitalization
 - If 2 consecutive study visits or 2 doses of IMP are missed during the course of the study

All participants who discontinue treatment should remain enrolled and complete their discontinuation visit within 8 weeks of last IMP. At that visit, although no longer receiving IMP, participants should be encouraged to complete all subsequent study visits and procedures. Data collection should continue according to the study protocol.

10.2 Lost to follow-up

A subject is considered lost to follow-up if they fail to return for scheduled study visits and are unable to be reached by study staff. This includes 3 attempts of either phone calls or emails; having sent 1 certified letter; or 1 unsuccessful effort to check the vital status of the subject using publicly available sources.

10.3 Study Withdrawal

Patients may withdraw study consent at any time without prejudice to further treatment. They may request destruction of collected samples, which will be completed and documented in study records.

11. Risk to Participants

Dupilumab is an add-on maintenance treatment in adult participants with uncontrolled CRSwNP. The most common adverse reactions that took place in 2 randomized, placebo-controlled, multicenter trials were injection site reactions, eosinophilia, insomnia, toothache, gastritis, arthralgia, and conjunctivitis.

Version: 3.7.3 2Apr2024

12. Potential Benefits to Participants

There are no direct benefits for participating in this study.

13. Compensation to Participants

Participants will be reimbursed a subject stipend for participating in the research study to help with the cost of expenses/travel for the research visit and to compensate for their time and effort. Participants will receive a stipend of \$50 after completing the following visits: V1, V3, V4, V5, V6, V7, and V8. They will also receive \$25 for each visit of dupilumab/placebo injection. If they complete all study visits, they will get a total of \$1000. The payment will be processed when participants come in person and will include that clinic visit' payment and injections payments since the last clinic visit. Each site will decide how participant stipends will be given to the subject.

14. Data Management and Confidentiality

The site-Investigator will ensure that all data are recorded appropriately and consistent with good clinical and research practice.

14.1 Sample Size and Power analysis

A sample size of 66 participants per group achieves 90% power to detect a mean difference of 2 points on the modified Lund-Kennedy Endoscopic score at 52 weeks with a standard deviation of 3.5 and significance level of 0.05 using a two-tailed test. The clinically meaningful mean difference of 2 points and the standard deviation are based on previous study of mLK in a heterogeneous population with nasal polyps [5].

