14.5 Statistical Approach

All data will first be assessed by the data management staff, under direction of the lead biostatistician, for missing data and out-of-range values with basic statistical procedures such as univariate statistics (means, standard deviations, ranges, frequencies, proportions, percentiles) and graphs such as histograms, box and whisker plots, scatter plots and Q-Q plots. In addition, plots may be produced of individual and average trajectories of all repeated measures over time according to assigned treatment. All questions of data quality and integrity will be investigated before any statistical modeling, as complete and accurate data are essential for unbiased estimates and confidence intervals.

Baseline and demographic characteristics will be summarized overall for all participants and when applicable, by treatment group. Univariate summary statistics will be provided for continuous variables and frequencies for categorical variables. Graphical methods mentioned above will be used to examine distributions and identify potential influential points. Data transformations for variables may be considered. The balance of baseline measures across the two treatment groups will be compared using appropriate 2-sample tests, including Wilcoxon rank-sum and t-tests, and Fisher's exact and Pearson Chi-square tests. All analyses will be

conducted using SAS version 9.1 for Windows (SAS Institute, Inc., Cary, NC). All analyses will be two-tailed with significance level of 0.05 and conducted using the intention-to-treat principle.

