14.6 Primary Analysis

To examine changes in the co-primary outcomes, the modified Lund-Kennedy score and the incidence of oral corticosteroid utilization per participant, a mixed effects longitudinal model will be fit that includes group (dupilumab, placebo) as a between participants factor and time (randomization through post-treatment period) as a categorical within participants factor plus their interaction term. Time is treated as categorical so that we can use the group-time interactions with the time main effect to estimate and test intent-to-treat (ITT) group differences at each time point, with 52 weeks as our primary ITT test. As randomization is stratified by site, site will also be included in the model. This mixed effects model allows incorporation of a random intercept term for each subject, different numbers of measurements (in case a visit is skipped), and the choice of appropriate variance-covariance structure. The mixed model will also permit identification of any significant changes in the post-treatment period from 52 to 64 weeks. This primary mixed model will incorporate all subject's randomized.

The primary objective will be assessed by testing this null hypothesis: treatment with Dupilumab post-surgery is equivalent to treatment with placebo post-surgery at 52-week end of treatment. The additional time point at 64 weeks is included in the model to ensure efficient evaluation of both co-primary outcomes at the EOT and 12 weeks after EOT. Significant changes between weeks 52 and 64 will be examined by linear contrast. We will test the following null hypotheses against two-sided alternatives:

- H₀₁: there is a lack of difference between the changes in mLK from baseline to 52 weeks and from baseline to 64 weeks for the untreated.
- H_{02} : there is a lack of difference between the changes in mLK from baseline to 52 weeks and from baseline to 64 weeks for the treated.
- H_{03} : the treatment effect dissipates between 52 and 64 weeks.

The primary estimand for the primary endpoint is the composite/treatment policy strategy. The intercurrent events will be handled as follows:

- Undergoing sinus surgery for AFRS: data after surgery will be assigned the worst possible score (composite strategy)
- Taking SCS or other rescue medications: data collected after use will be used in the analysis (treatment policy strategy)

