- Discontinuing treatment: all data collected after discontinuation will be used in the analysis (treatment policy strategy)

We will examine the treatment effect in the subgroup of patients with unilateral disease by recording patients' time until next sinus surgery. We will investigate differences in this subgroup by examining the Kaplan-Meier curves and utilizing the log rank test of the difference between treated and non-treated. If there is a difference between survival times, we will use the Cox proportional hazard model to account for other relevant covariates such as disease severity.

The Bonferroni correction will be used to account for multiple testing and ensure Type-I error rate remains nominal.

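### The 90% power in Section 14.1 uses two-sided 0.05, but Section 14.6 has two co-primary outcomes and a Bonferroni correction; at 0.025 each, power for mLK is about 84%

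*Combined protocol and SAP*

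**What the plan says.** Section 14.1 bases the sample size on mLK alone. It says that 66 per group "achieves 90% power to detect a mean difference of 2 points on the modified Lund-Kennedy Endoscopic score at 52 weeks". The remaining assumptions behind that figure are stated alongside it: "with a standard deviation of 3.5 and significance level of 0.05 using a two-tailed test". The section mentions no multiplicity adjustment, gives no power for a second outcome and makes no allowance for missing data. Section 8 gives the same total as the number randomised: "A total of 132 participants will be randomized".

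Section 14.6 applies one longitudinal model to "the co-primary outcomes, the modified Lund-Kennedy score and the incidence of oral corticosteroid utilization per participant". It estimates "group differences at each time point, with 52 weeks as our primary ITT test". The section closes with this sentence: "The Bonferroni correction will be used to account for multiple testing and ensure Type-I error rate remains nominal". Neither the set of tests being corrected nor the alpha for each test is given, and nothing says whether success requires one co-primary outcome or both.

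Section 14.5 sets a general rule: "All analyses will be two-tailed with significance level of 0.05 and conducted using the intention-to-treat principle".

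**The concern.** A Bonferroni correction over two co-primary tests gives each of them less than 0.05. The power in Section 14.1 is calculated with the whole 0.05 given to mLK, so the sample-size statement and the error-control rule do not describe the same test.

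Two things are at stake. The first is that the trial's stated chance of detecting a 2-point mLK difference is too favourable. The second is that the significance threshold for a primary endpoint is not fixed in writing. If the Week 52 mLK p-value fell between 0.025 and 0.05, Section 14.5 would support calling it significant, while the usual reading of Section 14.6 would not. That should be settled before unblinding.

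**Working it through.** **Inputs.** From Section 14.1: n = 66 per group, difference 2 points, SD 3.5, two-sided alpha 0.05. From Sections 4.7 and 14.4: 1:1 allocation. From Section 14.6: two co-primary outcomes and a Bonferroni correction. The equal split, 0.05 / 2 = 0.025, is an assumption because the documents give no per-test alpha.

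**Formula.** Two-sample t-test with df = 2n − 2 = 130. The noncentrality is λ = difference / (SD × √(2/n)). Power is the probability that a noncentral t with parameter λ exceeds the critical value t(1 − α/2, df); the opposite tail is negligible here.

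- Standard error: 3.5 × √(2/66) = 0.609.
- λ = 2 / 0.609 = 3.283.

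**Step 1: the stated figure.** At alpha 0.05 the critical value is 1.978 and power is 90.3% (normal approximation 90.7%). With 65 per group the t-test gives 89.9%, so 66 is the smallest number that reaches 90%. The statement is therefore correct at an unadjusted two-sided 0.05, with almost no slack.

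**Step 2: the same design at smaller alpha.** All rows use the t-test, 66 per group and SD 3.5.

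| mLK alpha | Example | Power for 2 points | Difference detectable with 90% power |
|---|---|---|---|
| 0.05 | no correction | 90.3% | 1.99 |
| 0.04 | 0.04 / 0.01 split | 88.5% | 2.05 |
| 0.025 | equal split over two tests | 84.4% | 2.17 |
| 0.0167 | three tests | 80.3% | 2.26 |
| 0.0125 | four tests | 77.2% | 2.33 |

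The normal approximation at 0.025 gives 85.1%.

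**Step 3: can any split keep 90%?** Solving for the alpha at which 66 per group gives exactly 90% yields 0.0481. That leaves 0.05 − 0.0481 = 0.0019 for the corticosteroid outcome, which is not a workable allocation for a co-primary endpoint.

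**Step 4: sample size for 90% at 0.025.** The t-test needs 78 per group, or 156 in total, against the planned 132.

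**Step 5: missing Week 52 data (secondary).** The documents give no loss rate, so the rates below are assumptions. The calculation counts only participants with Week 52 data, at alpha 0.025.

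| Assumed loss | Effective n per group | Power |
|---|---|---|
| 5% | 62.7 | 82% |
| 10% | 59.4 | 80% |
| 15% | 56.1 | 77% |

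**The case against.** The strongest reply is that Section 14.1 is a conditional statement that is true on its own terms, and that a correction with no stated family does not by itself fix any particular power. The Bonferroni sentence does not mention the co-primary pair. It comes straight after the paragraph on unilateral disease, and Section 14.6 also contains three hypotheses about Weeks 52 to 64 and tests at each time point. The correction might have been meant for those. Alternatively, co-primary might mean that both outcomes must succeed, in which case each could be tested at 0.05 and mLK power would stay at 90%.

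Part of this stands. There is no slip in the arithmetic of Section 14.1, and 84% depends on reading the correction as an equal split. An unequal split such as 0.04 / 0.01 costs less than two percentage points.

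The alternatives do not rescue the figure as the plan is written. A both-must-succeed rule appears nowhere, and it would make a Bonferroni correction unnecessary for the pair. Nothing confines the correction to the subgroup or to the Week 64 hypotheses, and a family that adds those to the mLK test lowers power further. The sentence closes the section that defines the two co-primary outcomes, and the amendment log for version 3.3 lists the added co-primary endpoint and the plan for Type I error control together. The pair is therefore the likelier family.

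On missing data, the objection is fair that a completers-only calculation is not the planned analysis. The mixed model, multiple imputation and data collected after discontinuation may recover some precision, but the documents do not say how much. The main result does not rely on the loss figures.

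**Conclusion.** The concern holds. The 90% in Section 14.1 applies to an unadjusted two-sided 0.05 test and is inconsistent with a Bonferroni correction covering both co-primary outcomes. With an equal split, power for a 2-point difference is about 84%, a shortfall of about 6 percentage points, before any loss of Week 52 data. This rests on the plan's own difference, SD and group size, and on taking the two Week 52 co-primary tests as the family. With that family, some shortfall follows from every practical split; its size depends on the split chosen.

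The consequence is limited. The treatment estimate is unaffected and Type I error is not inflated. The power statement and the primary test's threshold should nevertheless be corrected.

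**What to change.** - **Section 14.6:** name the Bonferroni family as the two co-primary Week 52 tests, give the per-test alpha (0.025 under an equal split), and say whether success requires one outcome or both. State whether the Week 52 to 64 hypotheses and the unilateral-disease comparison fall outside that family.
- **Section 14.5:** say that 0.05 is the family-wise level for the co-primary outcomes.
- **Section 14.1:** restate the power at the chosen alpha. For an equal split: 66 participants per group give about 84% power at two-sided 0.025 for a 2-point difference, or 90% for 2.17 points. Add an assumed rate of missing Week 52 data and the power that results.

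If the sponsor chooses a different split or requires both outcomes to succeed, the same three places should say so, with the power recalculated to match.

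The cost is wording only, and no added participants are needed if about 84% is acceptable. The downside is a less favourable stated figure: about 84%, or about 80% under an assumed 10% loss with no recovery from the model. Restoring 90% at 0.025 would instead take 78 per group (156 in total) before any allowance for loss.
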